4.1.5 Exposure Periods

The first exposure cycle starts on Day 1 of successful study drug insertion. A full exposure cycle is comprised of 28 days. One woman-year comprises thirteen 28-day cycles. The following exposure periods are defined for analysis in terms of planned study days and study cycles to facilitate the efficacy and certain safety analyses.

Exposure Period	Study Day of Period Start (PSTDY)	Study Day of Period End (PENDY)
Year 1 (Cycle 1- Cycle 13)	1	364
Year 2 (Cycle 14-Cycle 26)	365	728
Year 3 (Cycle 27-Cycle 39)	729	1092
Year 4 (Cycle 40-Cycle 52)	1093	1456
Year 5 (Cycle 53-Cycle 65)	1457	1820
First 2 Years (Cycle 1-Cycle 26)	1	728
First 3 Years (Cycle 1-Cycle 39)	1	1092
First 4 Years (Cycle 1-Cycle 52)	1	1456
5 Years (Cycle 1-Cycle 65)	1	1820

Type of Events and Study Day During an Exposure Period

ЕТҮРЕ	Event	Study Day of Event (EVTDY)		
A	Expulsion	Study Day of Expulsion date		
В	Expulsion followed by conception within 7 days	Study Day of Expulsion date		
С	Removal	Study Day of Removal date		
D	Removal followed by conception within 7 days	Study Day of Removal date		
Е	Pregnancy before expulsion	Study Day of Conception date		
F	Pregnancy before removal	Study Day of Conception date		
Н	Lost to follow-up without pregnancy, expulsion or removal	Study Day of Last Date Device in Situ.		
I	Complete period without pregnancy, expulsion or removal	Study Day of Period End Date		

Note: Removal due to partial expulsion will be treated as expulsion

Exposure Duration in Days (EXDUR):

if EVTDY-PSTDY>0 then EXDUR = min(EVTDY-PSTDY+1, PENDY-PSTDY+1); else EXDUR=.;

Exposure Duration in Cycles (NCYCF) = EXDUR/28

Number of Completed Cycles (NCYCC) = INT(NCYCF)

Number Relevant Cycles (NCYCR)

- =NCYCC+1 if last partial cycle is >=23 days
- =NCYCC+1 if last partial cycle ETYPE is B or D or E or F
- =NCYCC, otherwise.

Number of Cycles with back-up contraceptives (including emergency contraception) or no intercourse within the period or there is no diary data (NCYCEXCL):

Exclude from NCYCEXCL the cycle in which the subject had an on-treatment pregnancy (ETYPE is B, D, E, F).

Back-up contraceptives or intercourse history are recorded in subject's diary.

If there are missing values then they will be handled as follows:

Missing back-up contraceptive diary entries will be treated as no back-up contraceptive use.

Missing intercourse diary will be treated as no intercourse.

Number of Evaluable Cycles (NCYCEV) = NCYCR-NCYCEXCL

For cumulative time periods, calculate cycle number of event:

Cycle Number of Event (CYCLEN) = CEIL(NCYCF)

Cycle Number of Event after Compression (CYCLENAC)= CYCLEN-NCYCEXCL

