14 CONCOMITANT MEDICATIONS AND DEVICES

Concomitant medications include any medication (any prescription medications or over the counter preparations) taken from the time the subject signs the informed consent/assent

documents until VeraCept removal/ expulsion or medications used to treat reportable SAEs occurring after study drug removal and must be recorded appropriately on the eCRF. In addition, concomitant medications used as prior contraception or used to treat a prior cervical infection within 30 days of informed consent/assent should also be reported.

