20.1 Analysis Populations

The following analysis populations will be created:

• Intent to Treat (ITT):

All subjects who underwent the study drug placement procedure, regardless of whether the study drug was successfully placed or not.

• Safety:

ITT subjects who had the study drug successfully placed

• Safety Subgroup (36-45 years):

Subjects in the safety population who were between 36 to 45 years of age (inclusive) at enrollment.

• Evaluable for Pregnancy (EP):

ITT subjects who had VeraCept placed successfully and meet requirements 1, 2 and 3 below. Subjects must also meet either requirement 4 or requirement 5 to be part of the EP study population:

- 1. Be post-menarcheal up to 35 years of age (inclusive) at enrollment
- 2. Have at least one report of pregnancy status after being enrolled
- 3. Do not have pre-treatment pregnancy, which is defined as the estimated conception date being before the insertion date.

AND

4. Have at least 1 cycle of e-diary with intercourse and without any backup contraception or emergency contraception (EC)

OR

5. Have an on-treatment pregnancy, which is defined as the estimated conception date being on or after the insertion date and no more than 7 days after the VeraCept is removed or expelled.

Subjects with major protocol violations that are deemed to have had a material impact on the primary efficacy assessment will be excluded from EP analysis population. Exclusions based on major protocol deviations will be reviewed and approved by Sebela and its designee.

• Evaluable for Cycle Control (ECYC):

ITT VeraCept subjects with at least one cycle for which:

1. A pregnancy did not occur;

AND

2. There was an assessment of bleeding reported by the subject.

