20.5 Pre-Trial and Concomitant Medications

Concomitant medications include any medication (any prescription medications or over the counter preparations) taken from the time of informed consent/assent until VeraCept removal/expulsion or medications used to treat reportable SAEs occurring after study drug removal. Pre-trial medications include any contraception used or treatment for a prior cervical infection within 30 days of informed consent/assent. The number and percentage of subjects using medications, as captured on the Concomitant Medication eCRF, will be tabulated according to the medication's World Health Organization Anatomical Therapeutic Drug Class and Generic Term. Pre-trial and concomitant medications will be presented separately.

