20.6 Primary Endpoint Analysis

The primary efficacy endpoint in the study is contraceptive efficacy through three years of use and will be analyzed using the Pearl Index with 95% confidence interval for women in the EP population. Cycles (defined as 28 days) during which no intercourse occurs, or backup methods of contraception (including emergency contraception) are used will be excluded from the primary analysis of the Pearl Index unless the subject had an on-treatment pregnancy in that cycle. If Cycle 1 is evaluable, it will be included in the analysis regardless of the timing of VeraCept insertion relative to the subject's last pre-insertion menses.

One year is defined as comprising thirteen 28-day cycles.

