4.9 Primary Endpoint Analysis

The primary efficacy endpoint is contraceptive efficacy through 3 years of use and will be analyzed using the Pearl Index with a 95% CI (CI) for women in the EP population.

The Pearl Index is defined as the number of on-treatment pregnancies per 100 women years. On-treatment pregnancy is defined as the estimated conception date being after the insertion date and no more than 7 days after the VeraCept is removed or expelled. One woman year is defined as comprising thirteen 28-day cycles.

Point estimate of Pearl Index:
$$x \times \frac{1300}{E}$$

95% CI: $\left(\frac{1}{2}\chi_{(0.025,2x)}^2 \times \frac{1300}{E}, \frac{1}{2}\chi_{(0.975,2(x+1))}^2 \times \frac{1300}{E}\right)$

where x is the number of on-treatment pregnancies and E is the number of 28-day evaluable exposure cycles and $\chi^2_{(p,df)}$ is the pth quantile of χ^2 -distribution with df degrees of freedom.

Cycles during which no intercourse occurs or backup methods of contraception (including emergency contraception) are used or there is no diary data will be excluded from the primary analysis of the Pearl Index unless the subject had an on-treatment pregnancy in that cycle. If Cycle 1 is evaluable, it will be included in the analysis regardless of the timing of VeraCept relative to the subject's last pre-insertion menses.

x =sum of PREGNANCY

E =number of Evaluable Cycles (NCYCEV)

Pearl Index point estimate and 95% CI will be calculated for Year 1, Year 2, and Year 3, separately, and for 3 years cumulatively.

The analysis will be repeated for the following subgroups

- Race (white, non-white)
- BMI group at enrollment
- Age group at enrollment
- Parity at enrollment

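### SAP 4.1.5 names only the e-diary as the source for back-up contraception and scores blanks as no use, so a cycle with eCRF-documented emergency or hormonal contraception can stay in the Pearl Index denominator (minor)

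*SAP*

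**What the plan says.** **The exclusion.** Under Protocol 20.6, cycles without intercourse, or in which "backup methods of contraception (including emergency contraception) are used will be excluded from the primary analysis of the Pearl Index", except a cycle with an on-treatment pregnancy. No data source is named. SAP 4.9 has the same rule and adds a third ground; it removes "Cycles during which no intercourse occurs or backup methods of contraception (including emergency contraception) are used or there is no diary data", with the same exception.

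**The derivation.** SAP 4.1.5 puts the rule into practice through NCYCEXCL, and E is the sum of NCYCEV = NCYCR − NCYCEXCL. On the source it says: "Back-up contraceptives or intercourse history are recorded in subject's diary". On gaps it says: "Missing back-up contraceptive diary entries will be treated as no back-up contraceptive use". A missing intercourse entry is scored as no intercourse. The same count sets the time variable of the compressed Kaplan-Meier analysis: "Cycle Number of Event after Compression (CYCLENAC)= CYCLEN-NCYCEXCL".

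**The other record.** Protocol 14 requires every prescription or over-the-counter medication, from consent until removal or expulsion, to be recorded on the eCRF. Protocol 20.5 tabulates medications "as captured on the Concomitant Medication eCRF". SAP 4.1.11 gives rules for their incomplete dates and SAP 4.7.7 summarises them. Neither document links these records to NCYCEXCL or says what to do when diary and eCRF disagree.

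**The concern.** The stated exclusion turns on use. The derivation turns on what the diary shows, and a blank counts as evidence of no use. The two can part when the trial holds a dated record of use that the diary lacks.

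The protocol itself foresees such a case. Under Protocol 12.11, emergency contraception may be given when expulsion is suspected. Under Protocol 4.5, a subject whose device is confirmed in place by ultrasound may continue. Protocol 13 gives her 7 days to enter each diary day, and the SAP revision history calls this a lockout. If the emergency contraception is not entered in time and the cycle has at least one recorded act of intercourse, the cycle counts in E although the eCRF may show the use. Confirmed expulsions are not the issue, because those subjects leave the study.

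At stake is the denominator of the primary endpoint in a single-arm trial, and with it the compressed Kaplan-Meier estimate. The latter uses the same classification, so it cannot serve as an independent check on it.

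**Working it through.** **1. The rule applied to test cycles.** Each is a 28-day cycle without pregnancy. SAP 4.1.5 as written excludes it if there is no diary data, no recorded intercourse, or any recorded back-up use.

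| Cycle | Result under SAP 4.1.5 |
|---|---|
| Intercourse on one day; diary blank on the day of emergency contraception | retained |
| Intercourse recorded; back-up entry blank | retained |
| Intercourse recorded; eCRF shows emergency contraception; diary says no back-up | retained |
| The only intercourse falls on a blank day | excluded |
| No diary data | excluded |
| Emergency contraception entered in the diary | excluded |

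The gap is confined to the first three rows, and it matters only where use actually occurred. In the third row the cause is the single named source; in the first two the blank rule also plays a part.

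**2. The plan's own figure.** Protocol 20.9 and SAP 3.7 expect 577 evaluable woman-years in Year 3 and an upper 95% limit no more than 1 above the index. With 13 cycles per woman-year, E = 577 × 13 = 7,501. By SAP 4.9, index = 1300x/E and upper limit = ½χ²(0.975, 2(x+1)) × 1300/E.

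| Pregnancies x | Index | Upper limit | Distance |
|---|---|---|---|
| 2 | 0.347 | 1.252 | 0.906 |
| 3 | 0.520 | 1.519 | 0.9995 |
| 4 | 0.693 | 1.775 | 1.082 |

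The planned figure is reproduced for up to 3 pregnancies in Year 3. The documents do not state the expected x, so every x used here is an assumption.

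**3. Direction.** A wrongly kept cycle adds to E and never to x. If a share f of E is wrongly kept, removing it multiplies both the index and its upper limit by 1/(1 − f). One cycle changes the index by 1/7,501 = 0.013% of its value.

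**4. Cycles needed to understate the Year 3 index by 0.01.** k = E − 1300x/(index + 0.01).

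| x | k | Share of 7,501 |
|---|---|---|
| 2 | 210.3 | 2.80% |
| 3 | 141.5 | 1.89% |
| 4 | 106.7 | 1.42% |

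**5. A range for f, with x = 3.** The documents give no value of f.

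| f | Index | Upper limit |
|---|---|---|
| 0 | 0.520 | 1.519 |
| 1% | 0.525 | 1.535 |
| 2% | 0.531 | 1.550 |
| 5% | 0.547 | 1.599 |

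**The case against.** The diary is the trial's chosen instrument for this item. The fourth requirement for the evaluable-for-pregnancy population is worded on the e-diary in both documents, and Protocol 13 collects additional birth control daily through Month 96. The SAP never says that the diary is the only admissible source, nor does it tell the programmer to disregard other evidence. A reader might infer that the SAP contradicts the protocol. It does not: Protocol 20.6 names no source, so SAP 4.1.5 is a narrower implementation with no rule for conflicting records.

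There are also controls. Under Protocol 12.4 to 12.7, sites verify sexual activity and the documentation of back-up methods at each scheduled visit and contact, roughly monthly through Month 35. Protocol 19.3 provides for verification of eCRF data against source for all subjects who undergo placement. These controls cannot reopen a locked diary day, but they make an unrecorded use less likely.

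The eCRF is not shown to be independent of the diary, because concomitant medications are themselves a diary item. That emergency contraception is entered there follows from the any-medication definition; no section says so expressly. The suspected-expulsion example also needs several steps to coincide.

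All of this stands and limits the priority. It does not remove the point: where a dated eCRF record does show use, the text as written still keeps the cycle.

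**Conclusion.** The point holds as a minor one. Read as written, SAP 4.1.5 retains a non-pregnancy cycle with recorded intercourse even when the Concomitant Medication eCRF documents emergency or hormonal contraception in it, which does not follow the stated exclusion. The effect on E, taken alone, is an increase or none. Its size is unknown and probably very small; the figures above give scale only and rest on the planned 577 woman-years and assumed pregnancy counts. The cumulative three-year index has a larger denominator, so each cycle matters less there.

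Two stronger readings are tempting.

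- A reader might infer that the missing-data rules as a whole favour the product. The documents do not support this: scoring missing intercourse as none, and dropping cycles without diary data, both shrink E. The net direction is not established.
- A reader might infer from the distance of 0.9995 at x = 3 that the precision statement fails once a few cycles are removed. But x = 3 is not stated in the plan, the number of affected cycles is unknown, and the distance of 1 is a planning expectation, not a success criterion.

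**What to change.** Amend SAP 4.1.5 as follows.

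- Count a non-pregnancy cycle in NCYCEXCL if the diary, or a Concomitant Medication eCRF record with complete dates, shows emergency or hormonal contraceptive use overlapping that cycle. Diary-recorded use of any other back-up method counts as now.
- Limit eCRF use to the period from the day after successful insertion through removal or expulsion. The limit is needed because Protocol 14 also puts contraception used before consent on that form.
- Apply the rule that missing means no use only when no such record exists.
- List records with partial dates, and do not assign cycles from dates imputed under SAP 4.1.11.
- Leave pregnancy cycles as they are.
- Do not draw on the site's concomitant-contraception review unless that record is shown to be dated.

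Optionally, add a sensitivity Pearl Index that also drops non-pregnancy cycles with a blank back-up entry on a day with recorded intercourse. State that it does not reach use on wholly missing diary days and may equal the primary result.

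The cost is a few lines of text and one merge, with no new data collection. E becomes slightly smaller and the interval slightly wider. Condom use that is not entered in the diary stays undetected. The SAP provided follows protocol version 3.0 and five years of follow-up, so the change can go into the revision that the eight-year protocol calls for. If the three-year analysis has already been run, the corrected count can be reported as a sensitivity result.

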4.1.6 Pearl Index

Pearl Index is defined as the number of on-treatment pregnancies per 100 women years. On-treatment pregnancy is defined as the estimated conception date being on or after the insertion date (must be a successful insertion) and no more than 7 days after the study drug is removed or expelled. One women year is defined as comprising thirteen 28-day cycles.

Point estimate of Pearl Index: $x \times \frac{1300}{E}$

where x is the number of on-treatment pregnancies and E is the number of 28-day evaluable exposure cycles

Cycles during which no intercourse occurs or backup methods of contraception (including emergency contraception) are used or there is no diary data will be excluded from the primary analysis of the Pearl Index unless the subject had an on-treatment pregnancy in that cycle. If Cycle 1 is evaluable, it will be included in the analysis regardless of the timing of study drug placement relative to the subject's last pre-insertion menses.

If ETYPE is B or D or E or F, then PREGNANCY = 1; else PREGNANCY = 0

x = sum of PREGNANCY

E = Number of Evaluable Cycles (NCYCEV)

4.1.7 On-Treatment Pregnancy Rate

On-Treatment Pregnancy Rate is defined as cumulative probability of on-treatment pregnancy at the end of each analysis interval. It is calculated as failure probability from a survival analysis.

Time variable:

CYCLENAC= Time to conception in cycles (compressed)

CYCLEN = Time to conception in cycles (uncompressed)

Event variable PREGNANCY as defined above.

4.1.8 Study Drug Expulsion Rate

The expulsion rate is defined as cumulative probability of device expulsion at the end of an exposure period. It is calculated as failure probability from a survival analysis.

Time variable

CYCLEN= Time to expulsion in cycles (uncompressed)

Event variable Expulsion

If ETYPE is A or B, then EXPULSION=1; else EXPULSION=0

Expulsion includes removal due to partial expulsion

4.1.9 Continuation Rate

Continuation rate is defined as the cumulative probability of study drug use at the end of a study period. It is calculated as survival probability from a survival analysis.

Time variable:

CYCLEN= Time to study drug discontinuation in cycles (uncompressed)

Event Variable DISCONTINUATION:

If ETYPE is A or B or C or D then DISCONTINUATION=1;

else DISCONTINUATION=0

Those lost to follow-up and became pregnant before removal or expulsion are censored.

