4.12.8 Cumulative VeraCept Continuation Rates

Cumulative VeraCept continuation rates for Years 1 through 5 will be estimated via Kaplan-Meier method for the Safety population. The complementary log-log transformation will be used to construct 95% CIs. The number and percentage of subjects with each reason for discontinuation will be summarized. The analysis will also by repeated by parity at enrollment.

Time to VeraCept discontinuation from successful insertion will be analysis variable.

- If a subject discontinued VeraCept because of desire of pregnancy, the subject will be censored at the cycle of removal.
- If a subject discontinued because of pregnancy, VeraCept should be removed. However, according to protocol, the study drug could be removed at the time of delivery. So, for consistency, the subject will be censored at the cycle of removal or conception if not removed.
- If a subject is lost to follow-up, she will be censored at the last cycle in which the study drug was known to be in place.
- If a subject completed the exposure period, the subject will also be censored at the cycle of the period end.

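### The continuation rate censors women who conceive before removal or expulsion, so it sits slightly above the probability of use that the SAP defines, and its two sections date the censoring differently

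*SAP*

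**What the plan says.** SAP 4.1.9 states the target: "Continuation rate is defined as the cumulative probability of study drug use at the end of a study period". The event rule is "If ETYPE is A or B or C or D then DISCONTINUATION=1", and every other event type is coded zero. The types come from the table in SAP 4.1.5. A to D are expulsions and removals, with or without a conception in the following 7 days. F is "Pregnancy before removal" and E is its counterpart for expulsion. For E and F the event day is the conception date, and the cycle number CYCLEN is computed from that day.

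SAP 4.1.9 then adds: "Those lost to follow-up and became pregnant before removal or expulsion are censored". The grammar could suggest women who were both lost and pregnant, but the event coding gives E and F a zero in any case.

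SAP 4.12.8 restates the rule. It begins "If a subject discontinued because of pregnancy, VeraCept should be removed", observes that the device may come out only at delivery, and concludes: "So, for consistency, the subject will be censored at the cycle of removal or conception if not removed".

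The protocol (section 20.7.3) asks for Kaplan-Meier continuation rates in the Safety population and gives no rule for pregnancy. Protocol section 18 allows the device to remain until delivery when its threads cannot be reached. Protocol section 4.4 rules out replacement after removal or expulsion.

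**The concern.** Censoring suits a woman whose later status is unknown. Kaplan-Meier assumes that she would have gone on like those still at risk. For types E and F the status is known: conception has occurred, and in many cases removal or expulsion is recorded afterwards. A woman who conceives and then has the device removed is not a user at the end of the year and cannot receive another study device. Yet she enters the estimate as a potential continuer. SAP 4.12.8 itself describes her as having discontinued.

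Continuation at each year is a named secondary tolerability endpoint. The rule can only raise it, and raises it more when more pregnancies occur. In addition, a programmer cannot follow both dating rules. SAP 4.1.5 and 4.1.9 together stop the clock at conception, whereas SAP 4.12.8 stops it at the cycle of removal and uses conception only if there is no removal.

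**Working it through.** **Direction.** The product-limit estimate is the product over cycles of (1 − d/n), where d is the number of events and n the number at risk. With the date held fixed, recoding a censored woman as an event raises d in her cycle and leaves n unchanged. Every factor is the same or smaller, so the censored version is never below the counted version.

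**Inputs.**
- Pregnancy rate λ: the Phase 2 cumulative 3-year Pearl Index of 0.73 per 100 woman-years, 95% CI 0.09 to 2.65 (protocol 1.1.3).
- Low anchor for Year 3 continuation: 620/1,480 = 41.9% (SAP 3.7).
- Low anchor for Year 5: 350/1,480 = 23.6% (SAP 3.7).
- Higher levels are assumptions, because the documents give no expected continuation rate. There is therefore no planned continuation figure to reproduce.

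**Input check.** The exact Poisson interval of SAP 4.9, with 2 pregnancies and an index of 0.73, gives 0.09 to 2.64. At 0.7349, which also rounds to 0.73, the upper limit is 2.65. The Phase 2 interval reproduces within rounding.

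**Formula.** With a constant pregnancy hazard λ, independent of other discontinuation, reported S(t) = S(t) with pregnancy counted × exp(λt).

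**Year 3 at 0.73.** exp(3 × 0.0073) = 1.0221.
- 41.9% × 1.0221 = 42.8%, an overstatement of 0.9 points.
- 60.0% (assumed) × 1.0221 = 61.3%, an overstatement of 1.3 points.

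**Other years and rates.**

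| Year | Continuation, pregnancy counted | λ per 100 woman-years | Overstatement (points) |
|---|---|---|---|
| 1 | 80% to 90% (assumed) | 0.73 | 0.6 to 0.7 |
| 3 | 41.9% | 0.09 to 2.65 | 0.1 to 3.5 |
| 3 | 60% (assumed) | 0.09 to 2.65 | 0.2 to 5.0 |
| 5 | 23.6% | 0.73 | 0.9 |
| 5 | 40% (assumed) | 0.73 | 1.5 |

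**Simulation.** A cycle-based Kaplan-Meier over 39 cycles with 2,000,000 subjects, at 0.73 per 100 woman-years and with loss to follow-up included, gave 60.1% with pregnancies censored and 58.8% with pregnancies counted. The true share still using was 58.7%. The gap of 1.3 points agrees with the formula.

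**The case against.** The rule is deliberate and disclosed, and SAP 4.12.8 gives its reason. Continuation is listed under tolerability, where a rate net of pregnancy is a recognisable choice. Method failure is not hidden, because it is the primary endpoint and has its own Kaplan-Meier analysis. The effect is also small beside sampling error: with 1,605 women and 42% continuation, the binomial 95% half-width is 1.96 × √(0.42 × 0.58/1,605) = 2.4 points, even before censoring.

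Most of this stands as a limit on importance, but it does not rescue the rule. Delayed removal is a reason to choose a date. And nothing in SAP 4.1.9 or 4.12.8 labels the rate as net of pregnancy: the stated target is use of the drug, and 4.1.9 counts removals without regard to reason.

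The size is open to fair challenge. If the Phase 2 index was built as SAP 4.1.6 builds this one, it includes types B and D, which already count as discontinuations, and it divides by evaluable cycles only. Both features push the computed overstatement up. This trial's Pearl Index is also confined to women aged 35 or under, whereas continuation covers the whole Safety population. In the other direction, 620/1,480 is a planning minimum that presumably also reflects loss to follow-up. True continuation may be higher, and the overstatement with it.

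A reader might infer three stronger points that the documents do not support:
- That it is inconsistent to count a conception just after removal (type D) but not one just before (type F). The order of events differs: in type D use had already stopped.
- That pregnancy always ends use of the device. Protocol section 18 lets it stay until delivery in some cases.
- That the reasons-for-discontinuation table ought to reconcile with the curve. A crude count and a censored estimate need not agree, and the censoring of losses to follow-up already separates them.

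**Conclusion.** The point holds in a limited form. The estimator does not match the definition in SAP 4.1.9, the mismatch can only favour the device, and the two SAP sections disagree on the censoring date. At the Phase 2 rate the overstatement is roughly 1 percentage point at Year 3. This assumes a constant and independent pregnancy hazard, the Pearl Index as a proxy for the rate of types E and F, and assumed continuation levels. A reader might take the 3.5 or 5.0 points at the upper Phase 2 limit as the likely bias. That limit rests on two pregnancies and only bounds the range. The primary Pearl Index is unaffected, secondary analyses are descriptive, and no continuation threshold is stated. The correction is worth making because it is cheap, not because it would change a conclusion.

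**What to change.** In SAP 4.1.9 and 4.12.8, set DISCONTINUATION=1 for types E and F, state one event date, and delete the wording that censors pregnancies. The simplest date is conception, since CYCLEN already derives from it under SAP 4.1.5. The present version can stay as a supplementary rate labelled net of pregnancy.

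With the conception date, this is a small change to the wording and the event coding and needs no new data. Dating at removal would need a new time variable. The reported rate becomes about 1 point less favourable, and a device kept until delivery is counted as discontinued at conception, which the text should say.

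A related conflict should be settled in the same edit. SAP 4.12.8 says "If a subject discontinued VeraCept because of desire of pregnancy, the subject will be censored at the cycle of removal", whereas SAP 4.1.9 counts every type C and D removal as an event. Until that is resolved, the rate will not be all-cause even with E and F counted.
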